#### **4.2 CRITERIA FOR OFFERING TO INITIATE TREATMENT IN STEP 3**

Clinical, virologic, and immunologic criteria, as specified below, will be used to determine whether initiation of ART is indicated in subjects who have been assigned to Arm 2 (ART to be initiated at 24 weeks after HIV diagnosis). Subjects who meet these criteria for initiation of therapy will be encouraged to start ART. If the subjects agree, they will initiate therapy, which will be provided by the study while they are study participants.

Subjects in Arm 2 (ART initiation at 24 weeks after HIV study enrollment) will be offered therapy if:

1. CD4+ T cell counts fall below 350 cells/mm^3 on 2 consecutive determinations at least 4 weeks apart.

OR

2. Participant progresses to WHO clinical stage 3 or 4 irrespective of CD4+ T cell count).

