Chemistry/LFT				X		X	X			X							X	
Lipid panel	X***						X			X							X	
Urinalysis	X			X			X			X							X	
Hepatitis B serology																		
STI testing	X						X			X							X	
CD4+/CD8+ cells count	X			X			X			X					X		X	
Plasma HIV-1 RNA	X	X	X	X	X	X	X	X	X	X					X		X	
Semen and rectal secretion collection	X	X	X	X	X	X	X	X	X	X					X		X	
Screening questionnaire - Demographics	X																	
AUDIT	X																	
Interviewer – Monthly questionnaire*	X			X		X	X	X	X				X	X	X	X	X	
Quarterly questionnaire**	X					X			X					X			X	
Pharmacy Refills				X		X	X	X	X				X	X	X	X	X	
Hair Sample	X					X			X					X			X	
Blood volumes (ml) for participants with immediate treatment	160	60	60	71.5	10	121.5	21.5	110	10	121.5	50	50	50	100	13	100	0	121.5
Blood volumes (ml) for participants with deferred treatment	230	60	60	71.5	0	201.5	21.5	190	10	201.5	50	50	50	100	13	100	0	121.5

\*Monthly interviewer-administered questionnaire containing: Timeline Follow Back (alcohol use and sexual behavior), Visual analog scale for ART adherence, and Medication adherence program choices

\*\*Quarterly questionnaire containing: Drug and alcohol use (drug use history, DAST 10, drinking expectancies); Mental health and wellbeing (RAND 12, Social support scale, Stigma scale, Stigma and disclosure, Partner notification, Intimate partner violence, 10 item CES-D, CID Mental health items on anxiety, stress & coping; Medical care (Hospitalization and ER use, Barriers to care, Access to care, Self-efficacy for ART use). \*\*\* These will be done within 72 hours.

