### **7.4.2.2 On-Study Evaluations**

On-study evaluations will occur according to the schedule of events as specified in Section 7.4.1. On-study evaluations will occur according to the schedule of events as specified in Section 7.4.1. according to whether the participant was enrolled before or after the approval of Amendment 1, of this protocol. A study visit will be considered missed if it is not completed before half of the time between the current and next study visit has elapsed.

. Study visit windows will be +/- 5 days for scheduled study visits.

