#### **7.4.3.7 Immunologic Studies**

1. CD4+/CD8+ T-cell subsets

A CD4+ T-lymphocyte percent of total lymphocytes and CD8+ T-lymphocyte percent of total lymphocytes should be performed in addition to the absolute CD4+ and CD8+ T cell counts at screening and for all visits at which CD4+/CD8+ T cell counts are required. Because of the diurnal variation in CD4+ and CD8+ cell counts, determinations for individual subjects should be obtained consistently in either the morning or the afternoon throughout the study, if possible.

NOTE: Each time a CD4+/CD8+ measurement is obtained, the local laboratory must perform a WBC and differential from a sample obtained at the same time.

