#### **7.4.3.8 Virologic Studies**

1. Plasma HIV-1 RNA

All HIV-1 RNA testing will be performed using the Abbott *m2000 RealTime* System (Abbott Molecular) at the IMPACTA PERU Clinical Trials Unit Central Laboratory, which

is certified by the U.S. NIH/NIAID/DAIDS Virology Quality Assurance (VQA) Program. The baseline value will be the HIV-1 RNA level at the entry evaluation.

The results from the analysis of Plasma HIV-1 RNA for the visits 0, 12, 24, 36, and 48 will be available at the next follow-up visit to guide the medical management decision-making for each participant, according to the HIV management standards.

The plasma samples for RNA HIV-1 determination from visits 1, 2, 4, 6, 8, 16, and 20 will not be processed in real time. Since these determinations are exclusively research purposes, the samples will be processed at a later time.

2. **Phylogenetic Analyses**

HIV-1 sequencing and phylogenetic analysis will be performed at The University of Washington Molecular Genetics Laboratory

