## **9.2 TOXICITY MANAGEMENT FOR LABORATORY ABNORMALITIES**

Grade 3 and 4 laboratory abnormalities should be confirmed by repeat testing preferably within 3 calendar days of receipt of results and before study drug discontinuation, unless such a delay is not consistent with good medical practice. All laboratory abnormalities that would lead to a change in treatment should be confirmed as soon as possible.

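### In Arm 2, a low week-12 CD4 count that does not follow a low week-4 count has no scheduled or required repeat until week 24, when deferred ART starts anyway

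*Combined protocol and SAP*

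**What the plan says.** **The rule.** Section 4.2 gives Arm 2 two routes to ART before week 24. One is CD4 below 350 "on 2 consecutive determinations at least 4 weeks apart". The other is progression to WHO stage 3 or 4, whatever the CD4 count. Participants who qualify are encouraged to start, and the study supplies the drug.

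**The schedule.** In the post-amendment table of Section 7.4.1, the row "CD4+/CD8+ cells count" is marked during deferral at weeks 0, 4, 12 and 24. Visits with a blood draw also take place at weeks 8, 16 and 20, without CD4.

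**Timing.** Section 7.4.2.2 states: "Study visit windows will be +/- 5 days for scheduled study visits". A visit is "considered missed if it is not completed before half of the time between the current and next study visit has elapsed".

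**Related text.**
- Sections 5.3.2 and 5.3.3 set no CD4 limit at entry, so a low count at week 0 is possible.
- Section 6.3.1.1 bars treatment in weeks 0 to 24 unless Peruvian criteria are met. Section 3.6.1 describes the Peruvian threshold as CD4 below 350 and states no confirmation rule.
- Under Section 7.4.2.4, an Arm 2 participant who starts ART without meeting criteria does not receive study medication.

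**The concern.** The CD4 rule is the stated immunologic way out of deferral. It needs a second low count at least 4 weeks after the first, but the scheduled gaps widen from 4 to 8 to 12 weeks. The last gap ends at the visit where deferral ends. A count that first falls below 350 at week 12 therefore has no scheduled confirmation while confirmation could still change anything.

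Unless the site orders an extra test, or the participant reaches WHO stage 3 or 4, the rule leaves this participant untreated for the second half of deferral. Choosing to start without meeting the criteria means going without study drug. Access to the exit thus depends on site initiative.

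Elsewhere the protocol writes its repeat tests down: HIV RNA in Section 4.4, lactate in 9.1.4, creatinine in 9.2.5 and phosphorus in 9.2.6. The CD4 rule has no such instruction.

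**Working it through.** The plan gives no figure to reproduce. This is a calendar check.

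**Inputs.** The rule is from Section 4.2, the CD4 weeks and blood volumes from the post-amendment table in Section 7.4.1, and the windows from Section 7.4.2.2.

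**1. Gaps between scheduled counts.** Weeks 0 to 4: 28 days (23 to 33 with the window, taking week 0 as fixed). Weeks 4 to 12: 56 days (46 to 66). Weeks 12 to 24: 84 days (74 to 94).

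**2. All eight patterns at weeks 0, 4 and 12,** with week 4 drawn on day 28 or later. Low means below 350. The last column assumes a conditional repeat at week 8 or 16 that also proves low.

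| Week 0 / 4 / 12 | Rule met now | With a low repeat |
|---|---|---|
| low / low / either (2 patterns) | week 4 | week 4 |
| not low / low / low | week 12 | week 8 |
| not low / low / not low | not met by week 24 | week 8 |
| low / not low / low | not before week 24 | week 16 |
| not low / not low / low | not before week 24 | week 16 |
| low / not low / not low | not met by week 24 | unchanged |
| none low | not met by week 24 | unchanged |

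On scheduled counts the rule can act before week 24 only through low pairs at weeks 0 and 4 or weeks 4 and 12. If week 12 is low and week 4 is not, it cannot, whatever week 0 showed.

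**3. Size.** The confirmatory draw moves from week 24 to week 16: 24 − 16 = 8 weeks, one third of the 24-week deferral. That is time to the draw. If the result is acted on at the following visit, ART starts at week 20: 24 − 20 = 4 weeks sooner.

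**4. A smaller window effect.** If 4 weeks is read strictly as 28 days, a week-4 draw on days 23 to 27 cannot confirm a low week 0, although it is in window. The next scheduled count is week 12; with the repeat it is week 8.

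**5. Feasibility of the repeat.** The latest in-window week-12 draw is day 84 + 5 = 89, and 89 + 28 = 117. The week-16 window is days 107 to 117, and that visit is missed only from day 112 + 14 = 126. For week 4: 28 + 5 = 33, and 33 + 28 = 61. The week-8 window is days 51 to 61, with the visit missed only from day 56 + 14 = 70. Both repeats fit existing visits.

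**6. Blood.** Week 36 (RNA and CD4) takes 13 ml and week 20 (RNA without CD4) takes 10 ml, which suggests about 3 ml for CD4. The row "Blood volumes (ml) for participants with deferred treatment" shows 201.5 ml at week 8 and 190 ml at week 16: 3/201.5 = 1.5% and 3/190 = 1.6%.

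**The case against.** **Nothing forbids a repeat.** Section 4.2 speaks of determinations, not scheduled ones, and the participant attends weeks 16 and 20 anyway. This stands: a reader might infer that the CD4 exit is impossible after week 12, and the documents do not support that. The defect is that the repeat is neither scheduled nor required.

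**Section 9.2 may already ask for one.** It says: "All laboratory abnormalities that would lead to a change in treatment should be confirmed as soon as possible". That sentence is not limited to Grade 3 or 4 results, but it sits under toxicity management and does not name CD4. A prompt repeat also cannot meet a 4-week minimum. Section 7.4.3.7 mentions CD4 at screening; a screening value could at most pair with week 0.

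**The Peruvian criteria may be a third route.** Sections 6.3.1.1 and 3.6.1 read together could let a single low count suffice. This objection has weight. A reader might infer that the gap is thereby closed, or that the two rules flatly contradict each other. Neither follows: Section 3.6.1 is background describing a guideline threshold, and its silence on confirmation does not establish a single-count trigger. It does show that Section 6.3.1.1 needs to name the governing rule.

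**The gain is modest and the frequency unknown.** Eight weeks is an upper limit, for one kind of CD4 pattern. The repeat also lets some Arm 2 participants start before week 24, inside the immediate-versus-deferred contrast. Both points stand, although the protocol's own rule already intends those starts.

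**The 3 ml is an inference.** Table volumes do not add up strictly by test: the pre-amendment table gives 21.5 ml at weeks 4, 8 and 12 alike, although the tests differ. The figure shows scale only.

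**Conclusion.** The point holds as a mismatch between a participant-protection rule and the schedule meant to operate it. With a low week 12 after a week 4 that was not low, the written schedule cannot confirm the count before week 24. The confirmatory draw comes 8 weeks later than existing visits would allow, and the possible gain in ART start is up to 8 weeks, or about 4 if results are acted on at the next visit.

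This rests on the post-amendment table. The pre-amendment table is misaligned in the text available, although its volumes (10 ml at weeks 16 and 20, 13 ml at week 36) also suggest no CD4 between weeks 12 and 24. Section 4.2 counts the 24 weeks both from diagnosis and from enrollment; counting from diagnosis puts ART at or before the week-24 visit, so the conclusion is the same.

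A reader might infer that many participants are affected, or that the viral-load comparison is biased. The documents support neither: they give no rate of low CD4 in Arm 2, and no effect on the primary analysis is claimed. This is a worthwhile, inexpensive correction.

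**What to change.** 1. **Section 4.2.** Require that any Arm 2 CD4 count below 350 during deferral that does not already complete the criterion be repeated at the visit about 4 weeks later, at least 28 days after the low draw. Allow the repeat to run past the +5-day limit while the visit is not yet missed. State that low values at two consecutive scheduled CD4 visits still qualify, whatever a conditional repeat between them shows. Without that sentence, a week-8 repeat that is not low would break a low week-4 and low week-12 pair and push confirmation from week 12 to week 16.
2. **Section 7.4.1.** Add conditional CD4 entries at weeks 8 and 16 for Arm 2. Section 7.4.3.7 says that with each CD4 measurement "the local laboratory must perform a WBC and differential from a sample obtained at the same time". Week 8 already has a CBC; week 16 needs the WBC and differential added.
3. **Section 6.3.1.1.** Point to Section 4.2 as the single governing criterion. Do not add the Peruvian criteria as a second trigger: if read as needing one low count, they would make the confirmation rule and the repeats largely redundant.

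**Cost.** A short amendment with no new visits. Each non-completing low value costs one CD4 test and roughly 3 ml of blood, with at most two such tests per participant. A few more Arm 2 participants may start ART before week 24, slightly reducing the separation between arms, as the existing rule already accepts.

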#### **4.3 MANAGEMENT OF RESISTANCE**

Plasma specimens will be stored for future testing, including HIV genotyping for antiretroviral resistance if failure to control viral load is observed during the study. Subjects with resistance to one component of the regimen may substitute another antiretroviral agent for that component (see Study Specific Procedures for recommended substitutions) but the substituted medication will be provided by the study. The substitute medication will be provided by the study while the volunteer is participating in the study.

#### **4.4 MANAGEMENT OF SUBJECTS WITH VIROLOGIC FAILURE OR PREMATURE TREATMENT DISCONTINUATION**

For subjects on immediate treatment (Arm 1), suboptimal virologic response will be defined as

the following:

1. Confirmed failure to achieve  $> 1 \log_{10}$  drop in HIV-1 RNA by week 16 of first antiretroviral regimen. If at week 16 there is a  $< 1 \log_{10}$  drop in HIV-1 RNA then the HIV-1 RNA test must be repeated as soon as possible, preferably within 2 weeks of receipt of the result.
2. Confirmed failure to achieve HIV-1 RNA level  $< 50$  copies/mL by week 24. If at week 24 HIV-1 RNA remains  $\geq 50$  copies/mL, then the HIV-1 RNA test must be repeated as soon as possible, preferably within 2 weeks of receipt of the result.
3. HIV-1 RNA  $> 400$  copies/mL on 2 consecutive measurements after having achieved HIV-1 RNA  $< 50$  copies/mL on 2 consecutive measurements separated by at least 14 days.

If suboptimal virologic response occurs, University of Washington Virology Laboratory will perform HIV genotyping on a sample drawn before discontinuation of therapy if HIV-1 RNA  $\geq 500$  copies/mL, in order to determine whether or not resistance has developed and, if so, to aid in construction of a new antiretroviral regimen. The substitute medication will be provided by the study while the participant remains in the study. If the HIV genotyping reveals no evidence of resistance and compelling arguments (i.e., substantially improved adherence or intercurrent illness to possibly explain increased viral load) the original treatment plan can be continued. Any decision to continue medications in the setting of suboptimal virologic response must be discussed with the Study Chair/Co-Chair. Further management in terms of whether or not to begin a new or altered regimen should proceed at the discretion of the local investigator consistent with standards of care, keeping in mind that subjects are previously antiretroviral naïve and that potential treatment benefits must be weighed against the risk of further limiting antiretroviral treatment options. Subjects will be asked to remain on study to complete all study evaluations, during this time and alternative ART regimens will be provided by the Study.

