#### ***6.3.7.4 Options for Medication Substitutions for Virologic Failure***

If a subject develops virologic failure on the study regimen further management based in clinical judgment should proceed at the discretion of the On-Site Principal Investigator in consultation with the Protocol Chair. .

Substitutions in antiretroviral regimens during the course of the study are at the discretion of the site investigator. It is the site investigator's responsibility to review all concomitant medications to ensure safety. The protocol pharmacist is available for discussion if questions arise.

[figure not shown]
The substituted medications will be provided by the study for the duration of time that the participant remains in the study.

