## **10 CRITERIA FOR DISCONTINUATION OF THE TREATMENT PROVIDED BY THE STUDY**

### **10.1 PERMANENT TREATMENT DISCONTINUATION**

- Drug-related toxicity (see section 9.0 Toxicity Management);
- Requirement for prohibited concomitant medications (see Section 5.3.3.);
- Clinical reasons believed life threatening by the Study Medical Director, even if not addressed in the toxicity management of the protocol;
- Suboptimal virologic response as defined in Section 4.4.;
- Subject repeatedly non adherent, to the extent that the physician believes it would not be in the subject's best interest to continue treatment;

The subjects who permanently discontinue treatment provided by the study according to the criteria described should continue a different ART regimen according to the standard of care currently in place. The study investigators will take necessary steps to ensure that the subjects continue on ART. Counseling will be provided with special emphasis on safety, and on efficacy of ART options to use in the future if the participant discontinues study ART, and does not continue with any other antiretroviral treatment.

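### Section 4.4 requires a prompt repeat test after a poor week-16 HIV-1 RNA response, but Section 7.4.3.8 defers the week-16 assay as research-only (minor; week 12 largely covers the gap)

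*Combined protocol and SAP*

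**What the plan says.** Section 4.4 defines suboptimal virologic response for subjects on immediate treatment (Arm 1). Criterion 1 is a confirmed failure to achieve a greater than 1 log10 "drop in HIV-1 RNA by week 16 of first antiretroviral regimen". It adds an instruction for anyone whose week-16 change is under 1 log10: "drop in HIV-1 RNA then the HIV-1 RNA test must be repeated as soon as possible". The stated preference is for this to happen no more than 2 weeks after the result arrives. Meeting the definition leads to genotyping if RNA is at least 500 copies/mL, and to discussion with the Study Chair or Co-Chair before medication is continued. Section 10.1 also lists "Suboptimal virologic response as defined in Section 4.4" among the grounds for permanently stopping study-provided treatment.

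Section 7.4.3.8 sorts the plasma RNA samples into two groups. The results that "will be available at the next follow-up visit to guide the medical management decision-making" are those of "Plasma HIV-1 RNA for the visits 0, 12, 24, 36, and 48". For the rest, "The plasma samples for RNA HIV-1 determination from visits 1, 2, 4, 6, 8, 16, and 20 will not be processed in real time", and the reason follows: "Since these determinations are exclusively research purposes, the samples will be processed at a later time".

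**The concern.** One section treats the week-16 value as a clinical trigger, and the other says that it has no clinical use. Timing the repeat from receipt of the result does not resolve this. If the sample is assayed at an unspecified later date, a repeat done as soon as possible after that is of no clinical value.

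At stake is early recognition of non-response. A participant with little virologic response at week 16 could stay viraemic on a failing regimen until the next result reported for care. Section 3.3.3 itself notes that failure can go unrecognised until the next clinical review and viral-load measurement.

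**Working it through.** The plan gives no figure to reproduce here. The check sets the visit weeks side by side and then works out the timing.

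**Inputs**
- Weeks named in Section 4.4: 16 (criterion 1) and 24 (criterion 2). Criterion 3, rebound after suppression, names no visit.
- Real-time list in Section 7.4.3.8: 0, 12, 24, 36, 48, each result available at the next follow-up visit.
- Deferred list in Section 7.4.3.8: 1, 2, 4, 6, 8, 16, 20.
- Visits around these points in Section 7.4.1: 12, 16, 20, 24, 28 in the original schedule; 12, 16, 20, 24, 25, 26, 28 after Amendment Letter #1. Weeks 25 and 26 carry 50 ml blood draws for immediately treated participants.

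**Step 1: which criteria are affected.** Week 16 is on the deferred list and not on the real-time list, so criterion 1 conflicts with Section 7.4.3.8. Week 24 is on the real-time list, so criterion 2 works as written. The baseline for the log10 drop is the entry value (week 0), also real-time.

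**Step 2: what week 12 covers.** The week-12 result is seen at week 16. A drop of more than 1 log10 by week 12 already meets a standard set by week 16. A smaller drop is known at the week-16 visit, when a prompt test could be requested. The one thing week 12 cannot show is a rebound between weeks 12 and 16.

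**Step 3: delay if the week-12 result is not acted on.** A real-time week-16 result would be seen at the next visit, week 20. The next result actually reported for care is week 24.
- Original schedule: seen at week 28; delay = 28 − 20 = 8 weeks.
- Amended schedule: seen at week 25, 26 or 28, depending on which counts as the next follow-up visit; delay = 25 − 20 = 5, 26 − 20 = 6, or 28 − 20 = 8 weeks.

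So the delay is 0 if the week-12 result is acted on, and about 5 to 8 weeks if it is not.

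**Step 4: effect on the analyses.** Section 11.5.3 includes week 16 among the plasma viral-load time points. The deferred samples are still assayed, so the trajectories and the per-subject summaries are unaffected, and no sample size or power figure depends on when the assay is run.

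**The case against.** The strongest reply is that care does not depend on the week-16 assay. Section 7.4.3.8 supplies the week-12 result expressly to guide management under HIV standards, and it arrives at the week-16 visit. Section 6.3.7.4 leaves management to the investigator in consultation with the Protocol Chair: "If a subject develops virologic failure on the study regimen further management based in clinical judgment". Section 7.4.3.9 allows genotyping on clinical judgment, and nothing forbids an unscheduled test. All of this stands, and it is why the point is minor. It does not make criterion 1 executable as written, because Section 4.4 itself attaches no threshold, repeat or action to week 12.

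Three stronger readings are tempting, and the documents do not support them.

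- **Participants will be left viraemic until week 24 or later.** That requires a clinician to disregard a week-12 non-response that the protocol provides for decision-making. It would be a lapse in execution and does not follow from the text. Nor must each site devise its own workaround: participants entering Step 3 are sent to two clinics of one institution, and plasma RNA is run at one central laboratory. The Study Specific Procedures, which are not among the documents, may also address the matter.
- **A headcount of those harmed.** Section 3.3.3 puts 90% of patients below 50 copies/mL at 4 months. One could apply the other 10% to 75 immediately treated participants (150/2, the low end of Section 11.3, assuming that all are randomised 1:1) up to 187.5 (125 + 125/2, the high end of Section 4.1, with all acute participants treated at once). The result is 7.5 to 18.8, or about 8 to 19. This bounds everyone who might fail criterion 1, and it is loose, since missing 50 copies/mL is far from dropping less than 1 log10. Its upper end also counts acute participants treated outside Arm 1. Those delayed are only the participants who fail and whose week-12 result is also ignored, a fraction for which the documents give no basis.
- **Loss of a mandatory stopping rule.** The repeat is mandatory, but the consequences are graded. Section 4.4 allows the original plan to continue after discussion with the Chair or Co-Chair, and Section 10.1 concerns study-provided treatment and directs a change to another ART regimen.

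**Conclusion.** The inconsistency is real: criterion 1 of Section 4.4 reads a sample that Section 7.4.3.8 withholds from care, and nothing in the text provided reconciles them. Its severity is minor. The delay is 0 if the week-12 result is acted on at week 16, and about 5 to 8 weeks otherwise. That range assumes that a real-time week-16 result would be seen at week 20, and that the week-24 result is seen between weeks 25 and 28. The number affected cannot be derived from the documents and is probably very small. Criterion 2 and the planned viral-load analyses are intact.

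**What to change.** In Section 7.4.3.8, move week 16 to the real-time list for participants on immediate ART, or at minimum for those whose week-12 drop is under 1 log10. Leave the Section 4.4 criterion unchanged. The full version makes the rule work as written for everyone it covers. The minimum version limits prompt assays to flagged participants but would still miss a rebound between weeks 12 and 16.

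Re-keying criterion 1 to week 12, with week 16 as the confirmatory sample, would obtain confirmation sooner. However, it changes when failure is assessed. That is a clinical choice and is not needed to cure the mismatch.

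The cost is a wording change plus prompt instead of batched assay of a sample already drawn and tested at the study's central laboratory. No extra visit or draw is needed beyond the repeat that Section 4.4 already requires.
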